### **2.5.5 Sensitivity analyses 2**

A second sensitivity analysis will be performed based on the subjects recruited under Amendment 1 to Amendment 4 protocol versions. The analysis will be performed like the main analysis of the primary endpoint.

The sensitivity analysis to address the primary objective will be based on the same primary estimand.

The analysis will be performed based on all available data in the FAS. Missing values caused due to unevaluable samples or early discontinuations will not be imputed.

### **2.5.6 Sensitivity analyses 3**

A third sensitivity analysis will be performed by excluding assessments after COVID-19 positive status at the subject level. The analysis will be performed similar to the main analysis of the primary endpoint.

The sensitivity analysis to address the primary objective will be based on the same primary estimand.

The analysis will be performed based on all available data in the FAS. Missing values caused due to unevaluable samples or early discontinuations will not be imputed.

### **2.5.7 Sensitivity analyses 4**

A fourth sensitivity analysis will be performed on all the subjects randomized in the study with and without the prespecified enrollment windows specified in the respective protocol (00, 1-4). The analysis will be performed similar to the main analysis of the primary endpoint.

The sensitivity analysis to address the primary objective will be based on the same primary estimand.

The analysis will be performed on 2 sub populations:

1. Outside enrollment window : This will consist of all subjects randomized in the study who did not meet the inclusion criteria #3, for the respective pre-specified protocol enrollment window ( protocol versions, 00, 1 – 4). No statistical analysis will be performed if the total number of subjects are less than 5 for this subgroup.
2. Within enrollment window : This will consist of the total FAS population excluding the subjects enrolled outside enrollment window.

The analysis will be performed based on all available data in the FAS. Missing values caused due to unevaluable samples or early discontinuations will not be imputed.

### **2.5.8 Supplemental analysis**

In this supplementary analysis the variables to be analyzed are: Achieving a pre-specified percent change from Baseline in NT-proBNP (binary). Three binary outcome variables will be created for subjects achieving a 25%, 50% and 75% decline in NT-proBNP (0-no, 1-yes). The dataset used in the primary analysis will be used to define these categorical variables using the NT-proBNP. Logistic regression model will be fitted. The odds ratio, CI and p-value will be provided for each analysis. The dependent variable will be achieving a target decline in NT-proBNP and the predictor of response will be treatment group and in-hospital/out-of-hospital randomization status.

In addition, an analysis of the primary endpoint will be performed with subjects randomized to Amendment 4 (yes, no) as an additional factor to the model mentioned in [Section 2.5.2](#).

The supplemental analysis will be based on the following estimand.

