12.4.3 Sensitivity and Supplementary Analyses

Sensitivity analysis

Robustness of the primary efficacy results will be explored by developing an algorithm to impute missing values in the primary analysis, except the baseline value. Baseline value will

not be imputed. When applicable, multiple imputations technique will be considered for replacing the missing values. Data will be analyzed using the same ANCOVA model used in the primary analysis.

A second sensitivity analysis will be performed based on the Amendment 1 patients only. The analysis will be performed like the main analysis of the primary endpoint.

Additional sensitivity analysis will be performed by excluding assessments after COVID-19 positive status (during the study) at the patient level.

Supplemental analysis

In this supplementary analysis the variable to be analyzed is: Achieving a pre-specified percent change from baseline in NT-proBNP (binary). Three binary outcome variables will be created for patients achieving a 25%, 50% and 75% decline in NT-proBNP (0-no, 1-yes). The dataset used in the primary analysis will be used to define these categorical variables. Also, like the primary analysis, the missing values will not be imputed for this analysis. Logistic regression model will be fitted. The odds ratio, confidence interval and p-value will be provided for each analysis. The dependent variable will be achieving a target decline in NT-proBNP and the predictor of response will be treatment group and in-/out-of-hospital randomization category.

In addition, analysis of the primary endpoint will be performed with patients randomized after Amendment 4 (yes, no) as an additional factor to the model mentioned in [Section 12.4.1](#).

Subgroup analyses

A set of pre-specified subgroups will be defined in the Statistical Analysis Plan to assess consistency of the primary efficacy result and effect of these subgroups on NT-proBNP.

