##### **Estimand 1**

Population: Defined through the appropriate inclusion/exclusion criteria to reflect the targeted study population currently hospitalized for or within 30 days of a WHF event (HFpEF decompensation). A WHF event (HFpEF decompensation) is defined as a hospitalization, emergency department (ED) visit or out-of-hospital urgent HF visit, all requiring IV diuretics.

Endpoint: Time-averaged proportional change between Baseline and weeks 4 and 8 in NT-proBNP

Treatment: The randomized treatment sacubitril/valsartan or valsartan

Intercurrent event: Using a treatment policy strategy to handle the intercurrent event of treatment discontinuation.

Summary measure: Difference between treatment in ratios of geometric means

The primary null hypothesis to be tested is the ratio of the geometric means of NT-proBNP (average of Weeks 4 and 8 divided by Baseline) for the sacubitril/valsartan and valsartan treatment groups are equal ( $H_{10}$ ) versus the alternative hypothesis that the ratio of the geometric means of NT-proBNP are not equal ( $H_{1a}$ ).

For NT-proBNP, the time-averaged proportional change from Baseline in a natural logarithmic scale will be analyzed using an ANCOVA model using data from Weeks 4 and 8 with treatment,

in-hospital/out-of-hospital randomization status, gender, and Baseline LVEF ( $\leq$  Median,  $>$  Median) as fixed effect factors, age and the logarithmic Baseline NT-proBNP as covariates.

The values from Weeks 4 and 8 will be averaged and the change from Baseline in log transformed NT-proBNP will be calculated as follows:

$$\ln(\text{average post dose value}) - \ln(\text{baseline value})$$

The estimated treatment effect in terms of ratios of geometric means, based on the least-squares (LS) means from the model, and the corresponding two-sided 95% confidence intervals (CIs) will be presented.

The geometric means (presented as a ratio to Baseline) will be calculated by exponentially back transforming the LS means based on the ANCOVA model as follows:

$$\exp(\text{LS mean})$$

The FAS will be used for the primary endpoint analysis.

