#### **Sample size for the primary endpoint**

This sample size of 450 subjects would have 85% power to detect a 23% reduction in the geometric mean of the proportional change from Baseline to an average of Weeks 4 and 8 in NT-proBNP for the sacubitril/valsartan treatment group. This 23% reduction in geometric mean is equivalent to -0.2614 in natural log scale ( $=\ln(0.77)$ ). The power is estimated assuming a two sided significance level of 0.05, a common SD of 0.85 for change in log transformed NT-proBNP and a 15% rate of missingness in NT-proBNP at baseline or at both Week 4 and Week 8.

nQuery Version 8.4.1.0 (2019) software package is used in calculating the power of the test.

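### The 25/50/75% NT-proBNP responder models omit log baseline NT-proBNP, which the primary ANCOVA includes, so chance baseline imbalance passes into the odds ratio and some power is lost

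*SAP*

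**What the plan says.** SAP 2.5.8 defines three yes/no outcomes from the primary analysis data set and fits a logistic regression to each; "the predictor of response will be treatment group and in-hospital/out-of-hospital randomization status". Protocol 12.4.3 names the same two terms: "the predictor of response will be treatment group and in-/out-of-hospital randomization category". The SAP therefore follows the protocol here.

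The primary model in SAP 2.5.2 (repeated in SAP 5.4.1) has treatment, in/out-of-hospital status, gender and baseline LVEF category as factors, with "age and the logarithmic Baseline NT-proBNP as covariates".

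The responder analysis has its own estimand in SAP 2.5.8. Its summary measure is an odds ratio, and the text does not say whether that is conditional or marginal. No reason is given for the shorter model. SAP 1.1 states that randomization is not stratified.

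**The concern.** Whether a patient reaches a 50% fall depends in part on where that patient started. The plan accepts this for the continuous endpoint by adjusting for log baseline NT-proBNP, then drops the term when the same change is dichotomized. Without stratification, only chance balances baseline NT-proBNP between the arms. If one arm starts higher, the responder odds ratio can move for that reason alone while the primary ANCOVA is protected. A reader who sees the two results side by side could then take a disagreement due to baseline as a disagreement about the drug. Leaving out a prognostic covariate also lowers the power of each responder comparison.

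**Working it through.** **1. The plan's own figure.** Inputs from SAP Section 3: "This sample size of 450 subjects would have 85% power to detect a 23% reduction"; "This 23% reduction in geometric mean is equivalent to -0.2614 in natural log scale"; "a common SD of 0.85 for change in log transformed NT-proBNP"; "a 15% rate of missingness in NT-proBNP at baseline or at both Week 4 and Week 8"; "assuming a two sided significance level of 0.05".

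- Evaluable per arm: 225 × 0.85 = 191.25.
- SE of the difference: 0.85 × √(2/191.25) = 0.0869.
- 0.2614/0.0869 = 3.01, and Φ(3.01 − 1.96) = 85%. The noncentral t with 191 per arm gives 85.0%.

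The stated 85% reproduces. The documents give no power for the responder models.

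**2. Responder rates.** With a normal log change, the rate for decline *d* is Φ((ln(1−d) − ln c)/0.85) on valsartan and Φ((ln(1−d) − ln c + 0.2614)/0.85) on sacubitril/valsartan, where *c* is the control-arm ratio to baseline. The plan does not give *c*. Two values are taken as assumptions from trials summarized in protocol 1.1: 835/862 = 0.97 (the phase 2 HFpEF trial) and 1 − 0.253 = 0.747 (the in-hospital HFrEF trial).

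| Decline | c | Valsartan | Sacubitril/valsartan | Responders in 382 | Unadjusted power |
|---|---|---|---|---|---|
| 25% | 0.97 | 0.381 | 0.502 | 169 | 66% |
| 25% | 0.747 | 0.502 | 0.623 | 215 | 66% |
| 50% | 0.97 | 0.218 | 0.318 | 102 | 60% |
| 50% | 0.747 | 0.318 | 0.435 | 144 | 65% |
| 75% | 0.97 | 0.055 | 0.099 | 29 | 36% |
| 75% | 0.747 | 0.099 | 0.163 | 50 | 46% |

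**3. Adjusted against unadjusted, by simulation.** About 1,500 trials per setting, 191 per arm. R² is the share of variance in the log change explained by log baseline and equals the squared correlation; the documents do not give it. R² of 0.1, 0.2 and 0.3 correspond to correlations of about −0.32, −0.45 and −0.55. In this run all four primary-model covariates were added, with age, sex and LVEF given no prognostic value. Power, unadjusted → adjusted:

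| Decline | c | R² 0.1 | R² 0.2 | R² 0.3 |
|---|---|---|---|---|
| 25% | 0.97 | 66.7 → 69.3 | 66.7 → 72.9 | 66.4 → 73.7 |
| 25% | 0.747 | 67.1 → 70.9 | 66.4 → 72.3 | 64.7 → 73.6 |
| 50% | 0.97 | 60.1 → 63.1 | 60.5 → 64.9 | 60.4 → 68.6 |
| 50% | 0.747 | 62.1 → 65.4 | 66.1 → 71.3 | 65.5 → 73.7 |
| 75% | 0.97 | 35.6 → 36.0 | 32.3 → 34.8 | 36.4 → 40.9 |
| 75% | 0.747 | 46.9 → 47.9 | 44.5 → 48.3 | 46.1 → 54.5 |

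With the SD of change fixed, unadjusted power does not depend on R². Its variation along a row is simulation noise: one standard error is √(0.66 × 0.34/1500) = 1.2 points. Both models were fitted to the same simulated trials, so the gains are steadier than the levels.

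For correlations of −0.3 to −0.5 (R² 0.09 to 0.25), the gain is about 2 to 8 points at the 25% and 50% thresholds and 0 to 4 at 75%. Extending the grid to R² 0.4 gives an overall range of about 0 to 14.

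**4. Where the gain comes from.** At 25% decline with c = 0.97 and R² 0.2, the mean log odds ratio goes from 0.503 to 0.583 and its SE from 0.209 to 0.227. The signal-to-noise ratio goes from 0.503/0.209 = 2.41 to 0.583/0.227 = 2.57. Over the full grid the SE rises by about 3 to 19%. If the adjusted model is instead standardized to a marginal odds ratio, the sampling variance falls by about 4 to 23% at the 25% and 50% thresholds and 0 to 11% at 75%.

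**5. Baseline imbalance.** One standard error of the arm difference in standardized log baseline is √(2/191) = 0.102 SD. A chance imbalance of two standard errors (0.205 SD) moves the planned log odds ratio by about 0.09 to 0.19 at the 25% and 50% thresholds. Against a mean of about 0.5, that is 18% to 38% of the effect. The correlation between imbalance and the unadjusted estimate is about 0.2 to 0.4; with log baseline in the model it is close to zero.

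**6. Model size at 75%.** With 29 to 50 responders, six predictors leave 29/6 = 4.8 to 50/6 = 8.3 responders each. The planned two leave 14.5 to 25. Adding log baseline alone leaves 29/3 = 9.7 to 50/3 = 16.7.

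**The case against.** The strongest defence is that the two-term model is a deliberate, protocol-specified choice. The same two terms serve the recurrent-event, renal and special-interest adverse event models (SAP 2.6.2.2, 2.6.2.3 and 2.6.2.7), and the covariate-rich model is kept for the ANCOVAs. The responder analysis is supplemental with its own estimand, and the primary ANCOVA already supplies a baseline-adjusted answer. All of this is true and limits the consequence. It does not explain why a change measured relative to baseline is adjusted for baseline in one analysis and not in the other.

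Four stronger readings are tempting, and the documents or the arithmetic do not support them.

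- *The unadjusted odds ratio is invalid.* Randomization keeps it valid, and its confidence interval already allows for chance imbalance.
- *Adjustment makes the odds ratio more precise.* That carries a linear-model result over to logistic regression. The SE of the conditional log odds ratio rises. Precision improves only if the target is held fixed, as with a standardized marginal odds ratio.
- *The shorter model saves nothing.* At 75% it avoids fitting six predictors to about 30 to 50 responders, and its target is close to a marginal odds ratio.
- *All four omitted covariates should go in.* The calculation supports log baseline NT-proBNP only. The case for age, sex and LVEF is consistency with the primary model.

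**Conclusion.** The omission is real and worth correcting, at low priority. Leaving log baseline NT-proBNP out of the responder models exposes the odds ratio to chance baseline imbalance and costs about 2 to 8 points of power at the 25% and 50% thresholds and 0 to 4 at 75%. These sizes rest on 191 evaluable patients per arm, a normally distributed log change with SD 0.85, a true ratio of 0.77, a control-arm ratio of 0.97 or 0.747, and a baseline-change correlation of -0.3 to -0.5. The last two are assumptions. A weaker correlation would make the gain smaller and a stronger one would make it larger.

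**What to change.** - Add log baseline NT-proBNP to all three logistic models in SAP 2.5.8. The other primary-model covariates are optional at 25% and 50% and best left out at 75%.
- In the supplemental estimand, state that the odds ratio is conditional on the model covariates, or standardize the adjusted model and report a marginal odds ratio.
- Record the change in SAP Section 4, because it departs from the model in protocol 12.4.3, and make it before the treatment codes are released.

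The data are already collected, so the cost is SAP wording and a small programming change. The downside is that the conditional odds ratio lies further from 1 with a slightly larger SE, and is not directly comparable with an unadjusted odds ratio from another trial. If the sponsor prefers the two-term model, a sentence justifying it and naming the target would be the minimum.

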### **Estimand**

Population: Defined through the appropriate inclusion/exclusion criteria to reflect the targeted study population currently hospitalized for or within 30 days of a WHF event (HFpEF decompensation). A WHF event (HFpEF decompensation) is defined as a hospitalization, ED visit or out-of-hospital urgent HF visit, all requiring IV diuretics.

Endpoint: Dichotomized (25%, 50% and 75% reduction) change from Baseline in NT-proBNP from Weeks 4 and 8

Treatment: The randomized treatment sacubitril/valsartan or valsartan

Intercurrent event: Using a treatment policy strategy to handle the intercurrent event of treatment discontinuation.

Summary measure: Difference between treatment in odds ratio

The values from Weeks 4 and 8 will be averaged and the change from Baseline in NT-proBNP will be calculated and the reductions categorized.

The analysis will be performed based on all available data in the FAS. Missing values caused due to unevaluable samples or early discontinuations will not be imputed.

### **2.5.9 Subgroup analyses**

All subgroups as defined in [Section 2.2.1](#) will be analyzed for the primary endpoint.

The subgroup analysis will be based on the same primary estimand.

- The analyses will be performed like the main analysis of the primary endpoint with the addition of an interaction term for the subgroup and treatment.

An interaction p-value will be generated from a likelihood ratio test comparing the interaction model to the model without the interaction.

- Forest plots will be produced including interaction p-values for treatment by subgroup interactions.

## **2.6 Analysis of secondary objectives**

All analyses will be performed on the FAS, unless otherwise specified.

### **2.6.1 Secondary endpoints**

Secondary endpoints include the following:

1. The composite hierarchical outcome consisting of a) time to CV death, b) number and times of HF hospitalizations during follow-up, c) number and times of urgent HF visits during follow-up, and d) time-averaged proportional change in NT-proBNP (from Baseline to Weeks 4 and 8)

2. The cumulative number of recurrent composite events overtime, ie, the total number of composite events of HF hospitalizations, urgent HF visits, and CV death.
3. Incidences of a composite endpoint of worsening renal function defined as:
  - renal death
  - reaching end-stage renal disease (ESRD)
  - $\geq 50\%$  decline in estimated glomerular filtration rate (eGFR) relative to baseline
4. Proportional change in NT-proBNP from Baseline to Week 8
5. Proportional change in hs-Troponin (high sensitivity) from Baseline to Weeks 4 and 8
6. Dosing levels and discontinuations
7. Incidence of adverse events of special interest during treatment
  - Incidence of symptomatic hypotension
  - Incidence of hyperkalemia (potassium  $> 5.5$  mEq/L)
  - Incidence of angioedema
  - Incidence of worsening renal function, defined as an increase in serum creatinine of  $\geq 0.5$  mg/dl and worsening of the eGFR by at least 25% (based on central laboratory data).

All these secondary endpoints will be analyzed using FAS and nominal p-values will be reported. There will be no adjustment for multiplicity.

### **2.6.1.1 Adjudication of Events**

Among the secondary variables above, some of them or their components need to be adjudicated to confirm the reported types and occurrences based on a unified criteria for analyses. The adjudication of these events is based on an adjudication process through an independent Endpoint Adjudication Committee (EAC). The role of the EAC is to ensure that all clinical outcomes are judged uniformly, using standard criteria and processes. Specific details regarding endpoint definitions can be found in the adjudication charter (ref CEC Charter, final version 16 July 2021).

All deaths, (re-)hospitalizations, and urgent HF visits will be adjudicated. The following events will be assessed by the EAC during the study:

- DEATH:
  - Cardiovascular Death
    - Fatal Myocardial Infarction (MI)
    - Heart Failure Death
    - Sudden Death
    - Presumed Sudden Death

- Presumed Cardiovascular Death
- Fatal Stroke
- Fatal Pulmonary Embolism
- Cardiovascular Procedure-Related Death
- Other Cardiovascular Death
  - Non-Cardiovascular Death
  - Undetermined Cause of Death
- HOSPITALIZATIONS:
  - Cardiovascular (CV) hospitalization
    - Hospitalization for Heart Failure
    - Possible Hospitalization for Heart Failure
    - Cardiovascular Hospitalization for a reason other than Heart Failure
    - Cardiovascular Hospitalization that cannot be further classified
  - Non-Cardiovascular (non-CV) Hospitalization
  - Undetermined Cause of Hospitalization
- URGENT HEART FAILURE VISITS

Urgent Heart Failure visits as defined in EAC charter :

Urgent, unscheduled office/practice or emergency department visit for heart failure management not requiring overnight hospitalization and associated with all of the following:

1. New or worsening signs and symptoms of heart failure, defined by the same criteria as for the heart failure hospitalization end point above and
2. Intravenous therapy directed at heart failure management

## **2.6.2 Statistical hypothesis, model, and method of analysis**

### **2.6.2.1 Analysis of secondary endpoint 1**

The composite hierarchical outcome consisting of below 4 variables

- a) time to CV death (Adjudicated by EAC),
- b) number and times of HF hospitalizations during follow-up (Adjudicated by EAC - only the confirmed events will be considered, i.e. HF hospitalizations meeting PARAGLIDE-HF criteria),
- c) number and times of urgent HF visits during follow-up (Adjudicated by EAC), and
- d) time-averaged proportional change in NT-proBNP (from baseline to Weeks 4 and 8)

This secondary efficacy endpoint of the composite hierarchical outcome will be analyzed estimating the unmatched win ratio by comparing every participant in the sacubitril/valsartan arm to every participant in the valsartan arm to determine a winner (unmatched pairing method). The estimated win ratio (the total number of wins in the sacubitril/valsartan arm divided by the total number of wins in the valsartan arm) will be calculated. The corresponding null and alternative hypotheses are:

$H_{20}$ : Win ratio is equal to 1, versus

$H_{2a}$ : Win ratio is not equal to 1.

A win ratio greater than 1 will be in favor of sacubitril/valsartan arm. The testing of hypothesis  $H_{20}$  and calculation of the corresponding two-sided 95% CIs will be performed.

A component will only be used as tie-breaker in the pairwise comparison between two subjects if the comparison of components with a higher priority resulted in a tie. For component a) the subject with the later time to CV death is the winner. For component, b) the subject with the smaller number of HF hospitalizations in time at risk that is common for both subjects (for definition see Section 2.6.2.1.1) is the winner. If the number of HF hospitalizations in the time at risk is common for both subjects it is tied, the subject with the later time of the last HF hospitalization is the winner. For component c) the same algorithm is applied as for component b). For component d), the subject with the larger decrease or smaller increase in the proportional change is considered a winner; if the ratio of the proportional changes from two subjects is between 0.75 and 1/0.75, then the pairwise comparison of the change in NT-proBNP is considered tied. This proportional change is equivalent to  $\pm 0.2876$  on the natural log scale  $\ln(0.75)$  and  $\ln(1/0.75)$ .

The analysis will be performed using the unmatched pair win ratio approach. Contributions of each component of the composite endpoint to the total number of winners used in the estimation of the win ratio will be reported. More details on win ratio approach are in [Section 5.4.2](#)

